## *Phase 2*

For Cohort 1 (patients with RET fusion-positive solid tumors who have progressed on or are intolerant to standard first-line therapy for their cancers), a true ORR of  $\geq 50\%$  is hypothesized when selpercatinib is administered to patients with such malignancies. A sample size of 55 patients is estimated to provide 85% power to achieve a lower boundary of a two-sided 95% exact binomial confidence interval (CI) about the estimated ORR that exceeds 30%. Ruling out a lower limit of 30% is considered clinically meaningful and consistent with the estimated response rates seen with approved targeted therapies in molecularly-defined patient populations who have failed prior therapies (e.g., osimertinib [Tagrisso®], crizotinib [Xalkori®], alectinib [Alecensa®], and others).

For Cohort 2 (patients with RET fusion-positive solid tumors without prior standard first-line therapy), a true ORR of  $\geq 55\%$  is hypothesized when selpercatinib is administered to such patients. A sample size of 59 patients is estimated to provide 85% power to achieve a lower boundary of a two-sided 95% exact binomial CI about the estimated ORR that exceeds 35%. For Cohort 3 (patients with RET-mutant MTC who have progressed on or are intolerant to vandetanib and/or cabozantinib), a true ORR of  $\geq 35\%$  is hypothesized when selpercatinib is administered to such patients. A sample size of 83 patients is estimated to provide 85% power to achieve a lower boundary of a two-sided 95% exact binomial CI about the estimated ORR that exceeds 20%. Ruling out a lower limit of 20% is considered clinically meaningful in patients who have failed prior MKI therapy (e.g., cabozantinib) and currently have limited treatment options for their advancing disease.

For Cohort 4 (patients with RET-mutant MTC who are MKI-naïve), a true ORR of  $\geq 50\%$  is hypothesized when selpercatinib is administered to such patients. A sample size of 55 patients is estimated to provide 85% power to achieve a lower boundary of a two-sided 95% exact binomial CI about the estimated ORR that exceeds 30%.

Notwithstanding the statistical considerations above, if approved by the SRC, enrollment beyond the above sample sizes in each of Cohorts 1-5, will be allowed, in order to accommodate enrollment demand and allow for the characterization of AEs that may occur with low frequency. With a sample size of 150 patients, the probability of observing one or more instances of a specific AE within a cohort with a true incidence rate of 1% and 2% is 77.9% and 95.2%, respectively. The sample size for Cohort 1 was increased to ~250 to accommodate enrollment demand. Additional enrollment will also allow for the characterization of AEs that may occur with low frequency which would enhance knowledge of the safety profile of selpercatinib. Further, this cohort allows for the enrollment of patients with RET fusion-positive solid tumors other than NSCLC. While the enrollment demand for patients with RET fusion-positive NSCLC has been adequate for statistical analysis, additional solid tumor types remain underrepresented and enrollment expansion allows for data capture in this population.

Up to ~50 patients will be enrolled into Cohort 6 based on clinical consideration. Exploring efficacy in patients with a history of prior exposure to RET specific inhibitors may enhance

understanding of the risk:benefit of additional RET specific therapy in these patients and aid in the consideration of resistance mechanisms in response to this type of therapy.

#### 8.4 Futility Monitoring

A futility analysis of the response rate (including confirmed or unconfirmed PR or CR) will be performed after every 25 subjects are enrolled for each cohort of Cohorts 1-5. The purpose of the futility assessment is to safeguard future patients from exposure to unequivocally inferior treatment. A response rate of less than 10% (null hypothesis) is deemed as futile. The stopping boundaries are specified as following with Lan-DeMets (O'Brien-Fleming) spending function. If at least 1, 2, 7, 13 and 18 responders are observed from the first 25, 50, 75, 100 and 125 subjects enrolled, then enrollment will proceed without interruption. Otherwise, enrollment will be halted pending the results of each futility assessment. If the true ORR is at least 20%, the probability of stopping at each futility analysis is less than 3%. If the true ORR is significantly higher than that hypothesized (i.e., 50%) the probability is close to zero.

The information fractions and futility boundaries based on a sample size of 150 patients are outlined in [Table 8-1](#).

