- Cohort 4 (up to ~125 patients): *RET*-mutant MTC without prior standard first-line cabozantinib or vandetanib or other kinase inhibitors(s) with anti-RET activity (see [Appendix A](#) for examples, for countries and sites where approved; Germany and South Korea is excluded).
- Cohort 5 (up to ~200 patients):
  - Cohorts 1-4 without measurable disease;
  - MTC not meeting the requirements for Cohorts 3 or 4;
  - MTC syndrome spectrum cancers (e.g., MTC, pheochromocytoma), cancers with neuroendocrine features/differentiation, or poorly differentiated thyroid cancers with other *RET* alteration/activation may be allowed with prior Sponsor approval;
  - cfDNA positive for a *RET* gene alteration not known to be present in a tumor sample.
- Cohort 6 (up to ~50 patients): Patients who are otherwise eligible for Cohorts 1-5 who discontinued another RET inhibitor may be eligible with prior Sponsor approval.
- Cohort 7 (up to ~19 patients): Patients with a histologically confirmed stage IB-IIIa NSCLC and a RET fusion; determined to be medically operable and tumor deemed resectable by a thoracic surgical oncologist, without prior systemic treatment for NSCLC. This cohort was removed from study as of 01June2022. One patient from a site in the US was enrolled and has discontinued treatment.

[figure not shown]
These patients will be treated at the MTD if one is identified or at a lower dose level (i.e., the recommended dose for further study) chosen by the SRC that has a DLT rate < 33%, is safe, and is likely to provide RET target engagement (i.e., the observed drug exposure in patients at that dose is associated with preliminary evidence of efficacy and is in agreement with the exposure-efficacy relationship predicted from preclinical data). In addition, the dose chosen for Phase 2 may be changed by the SRC based on emerging data (e.g., PK, safety, and/or efficacy), as long as the new dose is not greater than the highest dose that has a DLT < 33% and is determined to be safe by the SRC in Phase 1. If the RP2D is changed, patients enrolled to Phase 2 at a different dose may have the dose changed to the new dose.

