**Table 8-4 Futility Assessment for a sample size of 50**

Look #	Information Fraction	Sample Size	Futility Boundary		Incremental Boundary Crossing Probabilities	
			Response Rate	Responder (n)	Under H0: $\pi = 0.1$	Under H1: $\pi = 0.2$
1	0.5	25	0.156	4	0.827	0.293

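### Section 8.4's under-3% stopping probability at a 20% ORR holds for Tables 8-1 to 8-3 but not for Table 8-4, and the only cohort that fits Table 8-4 (Cohort 6) is outside the stated futility scope

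*Protocol*

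**What the plan says.** Protocol Section 8.4 sets 10% as the futile rate ("A response rate of less than 10% (null hypothesis) is deemed as futile") and says a futility analysis "will be performed after every 25 subjects are enrolled for each cohort of Cohorts 1-5". It names the method: "The stopping boundaries are specified as following with Lan-DeMets (O'Brien-Fleming) spending function". It then gives the boundaries of the 150-patient design ("If at least 1, 2, 7, 13 and 18 responders are observed from the first 25, 50, 75, 100 and 125 subjects enrolled") and the consequence of missing one: "Otherwise, enrollment will be halted pending the results of each futility assessment". The operating characteristic follows directly: "If the true ORR is at least 20%, the probability of stopping at each futility analysis is less than 3"%. That sentence carries no restriction to a table, cohort or sample size.

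Table 8-1 covers a sample size of 150. The section then adds Tables 8-2, 8-3 and 8-4 for 250, 200 and 50 patients and applies the same continue-or-halt logic to each. The last, headed "Table 8-4 Futility Assessment for a sample size of 50", has one look at 25 patients, a response-rate boundary of 0.156, a requirement of 4 responders, and printed crossing probabilities of 0.827 at a true rate of 10% and 0.293 at 20%.

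Section 3.6 lists "Cohort 6 (up to ~50 patients"), and Section 8.3 says its size rests on clinical consideration. The SAP text does not take up futility monitoring.

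**The concern.** Section 8.4 gives two values for the same quantity. The text puts the chance of stopping at any look below 3% when the true ORR is 20% or more; Table 8-4 prints 29.3% at 20%. A reader who takes the sentence as covering the whole section gets the wrong operating characteristic for one of the four designs.

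The scope is also unsettled. The only cohort of about 50 patients is Cohort 6, and the sentence defining who is monitored leaves it out. From the protocol alone one cannot tell whether enrollment of patients who discontinued another RET inhibitor is subject to a futility look. At stake is the accuracy of a stated design property and the clarity of a rule that could pause a cohort. No efficacy estimate in the SAP depends on it.

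**Working it through.** **Inputs.** Look sizes, rate boundaries, responder counts and printed probabilities come from Tables 8-1 to 8-4. The 3% ceiling and the rates of 10% and 20% come from the text of Section 8.4 and the table headings. Cohort sizes come from Section 3.6. A look stops the cohort when responders fall short of the tabulated count.

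**Step 1: reproduce the printed figures.** The normal approximation at one look is Φ((b − p)/√(p(1 − p)/n)). For Table 8-4, b = 0.156 and n = 25.

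- p = 0.20: √(0.16/25) = 0.08; (0.156 − 0.20)/0.08 = −0.55; Φ = 0.291. Rounding of 0.156 (0.1555 to 0.1565) gives 0.289 to 0.293. Printed: 0.293.
- p = 0.10: √(0.09/25) = 0.06; (0.156 − 0.10)/0.06 = 0.933; Φ = 0.825. Printed: 0.827.

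For Table 8-1 at 20%, the same approximation, simulated over 25-patient increments, gives 0, 0.002, 0.009, 0.017 and 0.021, which matches the print. The printed values are therefore normal approximations to the rate boundaries.

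**Step 2: exact value for Table 8-4.** The rule in use is an integer rule: halt with 3 or fewer responders among 25.

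P(X ≤ 3) = Σ C(25, j) p^j (1 − p)^(25 − j), j = 0 to 3.

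At p = 0.20: 0.0038 + 0.0236 + 0.0708 + 0.1358 = 0.234.

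| True ORR | Exact probability of halting |
|---|---|
| 10% | 0.764 |
| 20% | 0.234 |
| 25% | 0.096 |
| 30% | 0.033 |
| 35% | 0.010 |
| 50% | 0.0001 |

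Against the 3% ceiling at 20%, the exact value is 0.234/0.03 = 7.8 times too large and the printed one 0.293/0.03 = 9.8 times. The exact value is still just over 3% at a true ORR of 30%.

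**Step 3: exact values for Tables 8-1 to 8-3 at 20%.** Let f_k(s) be the probability of reaching look k with s responders without having stopped. Each look adds an independent Binomial(25, p) count to the surviving totals; the stop probability at look k is the sum of f_k(s) over s below the required count.

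| Table | N | Largest single-look stop probability | Sum over looks |
|---|---|---|---|
| 8-1 | 150 | 0.023 | 0.052 |
| 8-2 | 250 | 0.004 | 0.008 |
| 8-3 | 200 | 0.007 | 0.018 |

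The under-3% sentence is correct for all three designs, taking each look's probability as incremental, as the table columns do.

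**Step 4: integer rule against print at look 1.** Tables 8-1 to 8-3 require at least 1 responder among 25 and print a crossing probability of 0. The exact probability of no responder is 0.9^25 = 0.072 at 10% and 0.8^25 = 0.004 at 20%.

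**Step 5: which cohort Table 8-4 fits.** Cohorts 1 to 5 have caps of about 250, 125, 125, 125 and 200. The power-based sizes in Section 8.3 are 55, 59, 83 and 55. None is 50. Cohort 6, at about 50, is the only match, and it is not among Cohorts 1-5.

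**The case against.** The strongest reply is that the sentence has a local scope. It directly follows the 150-patient boundaries and precedes the pointer to Table 8-1; for that design it is right, and it also holds for Tables 8-2 and 8-3. On that reading the defect is a missing qualifier. This largely stands, but the qualifier is needed because the section goes on to add a design for which the sentence fails.

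A reader might infer that Cohort 6 will be closed about one time in four while the protocol promises less than 3%. The documents do not support that. As written, futility analyses cover Cohorts 1-5 only, so the 23.4% applies to Cohort 6 only if the scope is resolved that way. Missing the boundary pauses enrollment pending the assessment; it does not by itself close the cohort. Nor is the figure hidden, since Table 8-4 prints 0.293. At the 50% ORR that the text also mentions, the exact value is about 0.01%, so the accompanying statement that stopping is then very unlikely holds.

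A reader might also infer that the boundary is wrong because 3/25 = 12% exceeds the 10% futile rate. A futility boundary may lie above the null rate, and the other tables do the same: 17/125 = 13.6% halts in Table 8-1, 29/225 = 12.9% in Table 8-2 and 23/175 = 13.1% in Table 8-3.

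Nor does the conflict show that the boundary should drop to 2 of 25. That would give 2.7% at 20%, but it would cut the stopping probability at 10% from 76% to 27%, weakening the protection that the section says it is for.

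The 7.2% at look 1 arises under the null rate, where stopping is intended, and does not touch the 3% statement. It shows only that the printed column does not describe the rule applied. Practical impact may also be small: the amendment history for version 11 records a decision to end enrollment to most populations, so the look at 25 may already have passed, though the documents do not say so.

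**Conclusion.** The point holds as an unqualified statement that fails for one of four designs, together with a scope mismatch. At a true ORR of 20% the stop probability under Table 8-4 is 0.234 exactly (0.293 as printed), against a stated ceiling of 0.03. Tables 8-1 to 8-3 satisfy the ceiling. Table 8-4 and the sentence limiting futility monitoring to Cohorts 1-5 cannot both be right as they stand, and they must be reconciled.

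The calculation assumes independent responses with a common rate, looks at exactly the tabulated sizes, and halting whenever the count is short. The documents do not show that the boundary is mis-set, that any cohort was wrongly paused, or what ORR would matter in Cohort 6, for which Section 8.3 gives no target.

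**What to change.** 1. Limit the under-3% sentence to the designs in Tables 8-1 to 8-3.
2. State whether Cohort 6 is under futility monitoring. If it is, add it to the scope sentence and give the exact probabilities of pausing enrollment under the 50-patient rule: 23.4% at an ORR of 20% and 76.4% at 10%. If it is not, delete Table 8-4.
3. Where crossing probabilities are printed beside responder counts, give exact values for the integer rules: for example 0.072 in place of 0 at look 1 under 10% in Tables 8-1 to 8-3 and, if Table 8-4 is kept, 0.764 and 0.234 in place of 0.827 and 0.293.

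The cost is an edit to one section and its tables, which can go into the next amendment. No boundary, sample size or data collection changes.

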**Table 8-1 Futility Assessment: Information Fractions and Futility Boundaries**

Look #	Information Fraction	Sample Size	Futility Boundary		Incremental Boundary Crossing Probabilities	
			Response Rate	Responder (n)	Under H0: $\pi = 0.1$	Under H1: $\pi = 0.2$
1	0.167	25	0	1	0	0
2	0.333	50	0.035	2	0.064	0.002
3	0.500	75	0.093	7	0.357	0.009
4	0.667	100	0.121	13	0.340	0.017
5	0.833	125	0.137	18	0.160	0.021

Note: The information fractions and futility boundaries are based on a sample size of 150 patients.

The information boundaries based on sample sizes of 250, 200 and 50 patients are outlined in [Table 8-2](#), [Table 8-3](#), and [Table 8-4](#), respectively. For each look, if the number of responders specified under the futility boundary is observed, enrollment will proceed without interruption.

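### Section 8.4 puts the chance of stopping at each futility look below 3% at a 20% ORR, but its 50-patient table prints 29.3% (23.4% exact), and the tabulated probabilities are not those of the printed responder counts

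*Protocol*

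**What the plan says.** Protocol Section 8.4 schedules a futility analysis that "will be performed after every 25 subjects are enrolled for each cohort of Cohorts 1-5". The null is defined by "A response rate of less than 10% (null hypothesis) is deemed as futile", and the tables use 20% as the alternative. On the boundaries it says: "The stopping boundaries are specified as following with Lan-DeMets (O'Brien-Fleming) spending function". The total error to be spent is not given.

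The 150-patient rule follows: "If at least 1, 2, 7, 13 and 18 responders are observed from the first 25, 50, 75, 100 and 125 subjects enrolled", enrollment continues. "Otherwise, enrollment will be halted pending the results of each futility assessment". The next sentence is the statement at issue: "If the true ORR is at least 20%, the probability of stopping at each futility analysis is less than 3" percent.

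Table 8-1 then gives the 150-patient design, and the text below it introduces designs for 250, 200 and 50 patients. It makes the responder count the decision rule for all of them: "For each look, if the number of responders specified under the futility boundary is observed, enrollment will proceed without interruption". Under the title "Table 8-4 Futility Assessment for a sample size of 50" there is a single look at 25 patients, with rate boundary 0.156, 4 responders, and crossing probabilities 0.827 (ORR 10%) and 0.293 (ORR 20%).

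**The concern.** There are two separate problems.

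First, a general statement of below 3% per analysis stands in the same section as a table whose only look shows 29.3% under the same alternative. One of them needs a qualifier.

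Second, the probability columns should describe the rule that triggers a halt, and that rule is a count. A look that requires at least 1 responder in 25 cannot have a crossing probability of exactly zero, yet Tables 8-1 to 8-3 print zero there.

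At stake is whether the protocol's stated operating characteristics can be relied on when a look is interpreted, above all the 50-patient look. The boundaries themselves are not in question.

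**Working it through.** **Inputs.** Responder minima, rate boundaries and printed probabilities come from Tables 8-1 to 8-4. The response rates are 10% and 20%. Looks come every 25 patients. A halt occurs if responders fall below the printed minimum.

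**Step 1: reproduce the printed figures.** For Table 8-4, use a normal approximation at the printed rate boundary c = 0.156, P = Φ((c − p)/√(p(1 − p)/25)).
- ORR 20%: Φ((0.156 − 0.20)/0.08) = Φ(−0.55) = 0.291; printed 0.293.
- ORR 10%: Φ((0.156 − 0.10)/0.06) = Φ(0.933) = 0.825; printed 0.827.

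The remaining gap is rounding of c: 0.15645, which also prints as 0.156, gives 0.293 and 0.827. Sequential simulation of the same approximation at the Table 8-1 rates gives, at ORR 10%, 0 / 0.063 / 0.358 / 0.341 / 0.158, against printed 0 / 0.064 / 0.357 / 0.340 / 0.160. The columns therefore belong to a continuous rate boundary.

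**Step 2: exact value for the printed 50-patient rule.** Halt if X ≤ 3, with X ~ Binomial(25, p).
- p = 0.20: 0.0038 + 0.0236 + 0.0708 + 0.1358 = 0.234.
- p = 0.10: 0.0718 + 0.1994 + 0.2659 + 0.2265 = 0.764.

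At other true rates the halt probability is 9.6% (ORR 25%), 3.3% (30%), 2.6% (31%), 0.97% (35%) and about 0.008% (50%). It falls below 3% only from a true ORR of about 31%.

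**Step 3: exact increments for the sequential designs.** At each look, add 25 Bernoulli outcomes to the distribution of responders among paths still continuing, take the mass below the minimum as the increment, and remove it.

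Table 8-1 (150 patients):

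| Look | Minimum | ORR 10% printed | ORR 10% exact | ORR 20% printed | ORR 20% exact |
|---|---|---|---|---|---|
| 1 | 1 | 0 | 0.072 | 0 | 0.0038 |
| 2 | 2 | 0.064 | 0.014 | 0.002 | 0.0001 |
| 3 | 7 | 0.357 | 0.298 | 0.009 | 0.0034 |
| 4 | 13 | 0.340 | 0.422 | 0.017 | 0.0216 |
| 5 | 18 | 0.160 | 0.127 | 0.021 | 0.0232 |

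The look-1 value is simply P(0 of 25): 0.9^25 = 0.072 and 0.8^25 = 0.0038. The same first look appears in Tables 8-2 and 8-3, also printed as zero.

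**Step 4: all designs against the 3% statement, and totals.**

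| Design | Largest increment at ORR 20%, printed / exact | Total at ORR 10%, printed / exact | Total at ORR 20%, printed / exact |
|---|---|---|---|
| 150 | 2.1% / 2.3% | 92.1% / 93.2% | 4.9% / 5.2% |
| 250 | 0.2% / 0.38% | 93.5% / 94.0% | 0.5% / 0.8% |
| 200 | 0.7% / 0.65% | 92.9% / 93.5% | 1.6% / 1.8% |
| 50 | 29.3% / 23.4% | 82.7% / 76.4% | same (one look) |

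**Step 5: scope.** Section 3.6 caps Cohorts 1 to 5 at about 250, 125, 125, 125 and 200 patients. The only cohort of about 50 is Cohort 6, which lies outside the Cohorts 1-5 futility scope of Section 8.4.

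**The case against.** The sentence comes straight after the 150-patient rule, before any other design is mentioned, so it can be read as describing those five looks only. On that reading it is true, both as printed and exactly. Table 8-4 does not hide its 29.3%. The normal-approximation columns sit beside a rate boundary and are approximations, not slips. In Tables 8-1 to 8-3 the totals differ by about a point or less, and the increments at ORR 20% differ by no more than about 0.006. Missing the count halts enrollment pending assessment and does not close the cohort. Table 8-4 may govern no monitored cohort.

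All of this stands, and it limits the point. It does not remove it: the wording covers each futility analysis, the section contains four designs, and the text below Table 8-1 applies the count rule at each look, the 50-patient one included.

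A reader might infer more than the documents support:
- **That active cohorts will be wrongly closed.** Section 8.4 provides only a pause. At the ORRs hypothesized in Section 8.3 for Cohorts 1-4 (35% to 55%), the 50-patient rule would halt less than 1% of the time. No ORR is hypothesized for Cohort 6.
- **That a reviewing committee would take 3 of 25 as near-certain futility.** Section 8.4 names no decision body, and Table 8-4 shows its reader a halt probability higher than the exact one.
- **That the boundaries are wrong.** Nothing here changes a printed count.

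**Conclusion.** The point holds as a correction to stated operating characteristics. The below-3% statement is right for the 150-, 200- and 250-patient designs and wrong for the 50-patient design, by a factor of about ten on the printed figure and about eight on the exact one. The printed probabilities in all four tables are not those of the counts that decide a halt. The discrepancy is largest in the ORR 10% columns (0 against 0.072 at look 1; 0.340 against 0.422 at look 4 of Table 8-1) and in Table 8-4 (0.827 / 0.293 against 0.764 / 0.234). It is small in the totals of Tables 8-1 to 8-3.

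The exact figures assume independent patients with a common response rate, looks at exactly 25-patient steps with response known for everyone counted, and every missed count treated as a stop. The practical effect of the 50-patient error depends on whether Table 8-4 is used at all, which the text does not settle.

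**What to change.** In Protocol Section 8.4:
- Limit the below-3% sentence to the 150-, 200- and 250-patient designs.
- State that the 50-patient look halts enrollment with probability about 23% at a true ORR of 20% and about 76% at 10%.
- Replace the probability columns of Tables 8-1 to 8-4 with exact binomial values for the printed counts, including non-zero first-look entries.
- Reconcile Table 8-4 with the Cohorts 1-5 scope: either say which cohort it serves or remove it.

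No change of boundary is proposed. The cost is wording and table edits, with no extra patients or data. Some stated figures become less favourable (the 50-patient halt probability at a 10% ORR falls from 82.7% to 76.4%) and others more favourable (at 20% it falls from 29.3% to 23.4%).
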